#### 4.5.2 Secondary Endpoint Assessments

Secondary endpoints include:

- Annual rate of moderate or severe COPD exacerbations over the 12 month observation period
- Time to first severe COPD exacerbation over the 12 month observation period
- Annual rate of severe COPD exacerbations over the 12 month observation period
- Proportion of patients with moderate or severe COPD exacerbations over the 12 month observation period

The secondary analyses for these secondary endpoints will use the COPD exacerbation defined as moderate or severe (as applicable) as collected in the eCRF and defined in section 4.5.1 above. All moderate and severe exacerbations with onset until time of planned EOS visit at 12 months will be included in these analyses.

CONFIDENTIAL

#### 5.0 STATISTICAL ANALYSES

The following populations are defined for analysis and reporting. Before the database lock, the team will review only table shells, not populated with actual data, to avoid bias.

# 5.1 Analysis Populations

#### 5.1.1 Intent to Treat (ITT) Population

[figure not shown]
The ITT population includes all randomized patients allocated to their original randomized treatment group.

#### 5.1.2 Per Protocol (PP) Population

No per-protocol set is defined and no analysis is planned.

Version 3.0 March 2021

CONFIDENTIAL

The Safety population includes all randomized patients who received a prescription of any study treatment (Stiolto Respimat or triple therapy).

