#### **On-Study** Treatment

Triple therapy is defined as any of the combination of ICS, LABA and LAMA drugs that a patient's physician chooses. Therefore, the following combination of COPD medications categories will count as triple therapy on study, differentiating between free combination and FDC:

- Triple Therapy Free Combinations
  - $\circ$  ICS + LABA + LAMA
  - ICS-LABA + LAMA
  - ICS + LAMA-LABA
- Triple Therapy FDC
  - o LAMA-LABA-ICS

Patients may switch or discontinue study treatment over the 12 month observation period.

For the purpose of analysis, patients will be classified as Continued Original Randomized Treatment, Continued In-Class Randomized Treatment, or Off Randomized Treatment as described below. The categories are non-overlapping. Changes in targeted COPD concomitant medications do not apply to this classification.

- **Continued Original Randomized Treatment**: Patients taking the same COPD medication as originally initiated for randomized COPD study treatment.
  - Stiolto Respimat patients taking Stiolto Respimat.
  - Triple Therapy patients taking the same individual components of ICS plus LAMA plus LABA as initiated at Baseline.
- Continued In-Class Randomized Treatment: This definition only applies to Triple Therapy patients who made changes to the triple therapy components originally initiated for their randomized COPD study treatment (i.e., those not considered "Continued Original Randomized Treatment").
  - Triple Therapy patients taking any combination of ICS plus LABA plus LAMA that meets the study definition of triple therapy will be considered "Continued In-Class Randomized Treatment" if changed from original study medications.

•

- **On Treatment**: Patient is categorized as Continued Original Randomized Treatment or Continued In-Class Randomized Treatment (the duration of time is from randomization until the patient is no longer in one of these two categories)
  - Patients who have a temporary treatment interruption of  $\leq 28$  days will still be considered On Treatment provided they resume treatment that meets the On Treatment definition within 28 days of when the treatment was first interrupted.
    - If the On Treatment study medication is resumed with a new start date ≤ 28 days of the stop date, it will be classified as a temporary treatment interruption.

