#### 6.3 Reporting and Analysis Periods

AEs and SAEs will be reported from the time a patient signs consent until the EOS visit at 12 months or until the patient discontinues the trial. However, only "on treatment" AEs and SAEs will be included in analysis. "On treatment" medications for each treatment arm are defined in section 4.4.2. For the safety analysis time period, all AEs will be considered "on treatment" (see section 4.4.2) if the AE start date is within 21 days after the On Treatment study medication end date or until EOS, whichever comes first.

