# 7.0 IMPORTANT PROTOCOL VIOLATIONS (IPVs)

IPVs will be reported in a listing. Potential IPVs include:

- Inclusion or Exclusion criteria not met.
- Informed Consent not documented prior to study randomization.
- Initial prescription provided for randomized study treatment was incorrect. (This does not include changes to study medication subsequent to initiation of study treatment.)

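### A patient started and kept on the other arm's regimen counts in the safety denominator, but the SAP's On Treatment rule leaves that patient's AEs and SAEs out of the safety tables

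*SAP*

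**What the plan says.** - **Who is counted (SAP 5.1.4, Safety Population).** "The Safety population includes all randomized patients who received a prescription of any study treatment (Stiolto Respimat or triple therapy"). Protocol 6.2.2 says the same. A prescription of either regimen qualifies, whichever arm was assigned.
- **Which events are counted (SAP 6.3).** Events are gathered from consent to the end-of-study visit or discontinuation from the trial, but only those on treatment "AEs and SAEs will be included in analysis". The section takes the on-treatment medications for each arm from SAP 4.4.2, and adds 21 days after the On Treatment medication ends, cut off at end of study.
- **What On Treatment means (SAP 4.4.2, On-Study Treatment).** "Patient is categorized as Continued Original Randomized Treatment or Continued In-Class Randomized Treatment". The period is described this way: "the duration of time is from randomization until the patient is no longer in one of these two categories". For the Stiolto arm the first category is "Stiolto Respimat patients taking Stiolto Respimat". For the triple arm it is the same three components as at Baseline. The in-class category is reserved for triple-therapy patients and needs all three drug classes.
- **Wrong prescriptions (SAP 7.0).** One potential important protocol violation is "Initial prescription provided for randomized study treatment was incorrect". The visible text provides a listing of these and nothing more.
- **Table layout (SAP 6.4.1).** AE and SAE tables are by treatment group, a term that is not defined for safety.
- **Protocol 6.6.** The on-treatment period runs from the first dose of trial medication to 21 days after the last. Nothing there requires that medication to be the one assigned.

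**The concern.** The denominator rule looks at what was prescribed. The numerator rule looks at whether the patient is taking what was assigned. A patient who is given the other arm's regimen and stays on it passes the first test and fails the second, so the patient counts as exposed and, in the tables, event-free.

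Such an error is plausible with open-label prescribing at a planned 400 or so community sites, and the SAP itself allows for incorrect initial prescriptions. At stake is a downward bias in the reported AE and SAE percentages, and the loss from the tables of harms that occurred on one of the two regimens under study. In the SAE and fatal-AE tables one missing patient can be visible: with about 351 patients per arm, one patient is 1/351.5 = 0.28 percentage points.

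**Working it through.** The plan gives no figure on this point, so there is none to reproduce. The check is a trace of the rules, followed by an illustration of size.

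**Do the arm labels in SAP 4.4.2 mean randomized arm?** Both qualifying categories are named as continued randomized treatment. The same Stiolto bullet appears again in the end-of-study classification in SAP 4.4.2. SAP 5.4 tabulates that classification for the ITT population by treatment group, and SAP 5.1.1 forms ITT groups by original randomization. Randomized arm is therefore the natural reading, although SAP 5.1.4 and 6.4 do not state it for safety.

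**Trace on that reading**

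| Randomized to | Started on | In denominator? | On Treatment? | Events tabulated? |
|---|---|---|---|---|
| Triple | Stiolto alone, kept | Yes | No: no ICS, so neither category fits | No |
| Stiolto | Triple regimen without Stiolto, kept | Yes | No: not taking Stiolto, and the in-class category is closed to this arm | No |
| Stiolto | Stiolto plus an ICS, kept | Yes | Yes, by the letter of the Stiolto bullet | Yes, under Stiolto |
| Either | Other regimen, later corrected | Yes | Fits a category after correction, but the only stated start is randomization | Undefined |

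The third row arises because SAP 4.4.2 accepts an ICS plus a LAMA-LABA product as triple therapy, and SAP Appendix B lists Stiolto as LAMA-LABA. In the fourth row, the 28-day interruption rule does not settle the matter, since it speaks of resuming a treatment and here the assigned one was never begun.

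In the first two rows the 21-day extension cannot help: the patient has no On Treatment medication, and so no end date from which to count.

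**Against Protocol 6.6.** If either study regimen counts as trial medication, the events in the first two rows are on treatment. The visible part of SAP 2.1, which lists changes to the planned analysis, does not mention a narrower window.

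**Size.** Let p be the true proportion of patients with an event, r the share of the arm in one of the first two rows, and n the arm size. Assume these patients have the same event risk as the rest of the arm.

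- Reported proportion = p × (1 - r)
- Patients with an event who are lost per arm = n × r × p
- n = 703/2 = 351.5, from the reduced sample size in SAP 4.2 and 1:1 allocation
- r and p are not in the documents. Assumed ranges: r from 0.5% to 5%, p from 5% to 20%

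| r | p | Such patients per arm (n × r) | Reported p × (1 - r) | Lost per arm (n × r × p) |
|---|---|---|---|---|
| 0.5% | 5% | 1.8 | 4.98% | 0.09 |
| 1% | 10% | 3.5 | 9.9% | 0.35 |
| 2% | 10% | 7.0 | 9.8% | 0.70 |
| 5% | 20% | 17.6 | 19.0% | 3.5 |

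**The case against.** A reader might infer something stronger: that every patient with a wrong initial prescription can never be On Treatment and loses every AE and SAE. The documents do not support that.

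- A Stiolto-arm patient given Stiolto plus an ICS meets the written Stiolto definition.
- A patient whose prescription is later corrected is in an undefined position, which is not the same as excluded.
- SAP 7.0 speaks of an incorrect prescription, not of the other arm's regimen. If the prescription was for neither study regimen, and no study prescription followed, the patient would not enter the safety population at all.

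Nor would it be right to say that the harms vanish. SAEs go to the sponsor's safety database, events are collected from consent to end of study, and SAP 6.4.1 plans a listing of all SAEs (although SAP 6.3 might restrict it too). The loss is confined to the analysis tables.

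It can also be argued that the SAP never says safety is grouped as randomized, that the lead sentence of the first category refers to the medication originally initiated, and that if groups were formed by regimen received no events would be lost. The public copy is incomplete around the safety population definition, so a grouping rule in missing text cannot be excluded; none appears in Protocol 6.2.2.

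The first set of points stands and limits the finding to patients kept on the other regimen. The argument about grouping lowers certainty but does not remove the problem. The labels in SAP 4.4.2 are used elsewhere for randomized arms, and if grouping by regimen received was meant, the visible text does not say so, and two programmers could produce different tables. Finally, safety is descriptive with no testing, so no inference is at risk, only the accuracy of the reported counts.

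**Conclusion.** The point holds for patients started and kept on the other arm's regimen. Read by randomized arm, the SAP keeps them in the safety denominator and leaves their AEs and SAEs out of the tables, which is narrower than Protocol 6.6. This rests on two readings: that the labels in SAP 4.4.2 denote randomized arms, and that trial medication in Protocol 6.6 covers either study regimen. The protocol does not define the term more narrowly in that section.

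The effect on percentages is probably small: over the assumed ranges, about 0.1 to 3.5 patients with an event lost per arm. The actual number of such patients is not in the documents. The change is still worth making, because it is cheap and because the SAE and fatal-AE tables are the ones where a single omitted patient matters.

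**What to change.** In SAP 5.1.4, 6.3 and 6.4:

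1. Form safety groups by the study regimen actually received.
2. For safety only, define On Treatment as time on either study regimen plus 21 days, in line with Protocol 6.6. Tying it to the initial prescription alone would not do: a patient corrected to the assigned regimen would then lose events occurring more than 21 days after the correction.
3. State to which group the events of a patient with a corrected prescription are assigned.
4. Keep randomized grouping for effectiveness.

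The cost is SAP wording and one derived variable. Protocol 5.2.2 already has treatment details recorded in the eCRF. Safety and ITT arm sizes would differ by a few patients. The wider window would also take in patients who start correctly and later move to the other regimen, so the assignment rule in item 3 should cover them as well.

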#### 5.2 Patient Disposition and Accountability

Patient disposition will be summarized for all enrolled patients. This will include the number and percentage of patients in the ITT

The number and percentage of patients who complete the full study observation period, defined as those who complete the end of study visit, will also be presented. Additionally, the primary reason for not completing the study observation period will be tabulated for patients who terminated participation in the study early.

#### 5.3 Demographics and Baseline Clinical Characteristics

Demographic and baseline clinical characteristics will be summarized for the ITT population overall and by treatment group. Frequencies and percentages will be calculated for gender, race, ethnicity, smoking status, COPD exacerbation history categories, CAT categories, and GOLD A-D Classification, as defined in section 4.4. The number and percentage of patients with at least one of the pre-specified comorbid conditions will also be summarized along with the relative frequencies of type of comorbid condition (congested heart failure, hypertension, coronary artery disease, peripheral vascular disease, cerebrovascular disease, type 1 diabetes mellitus (T1DM), type 2 diabetes mellitus (T2DM), depression/anxiety, osteoporosis, gastroesophageal reflux disease (GERD)). Descriptive statistics will be calculated for continuous variables (age in years, years with COPD, baseline blood eosinophil count and baseline CAT score), as described in section 4.1.

#### 5.4 Treatment Regimen

Pre-study COPD treatment regimen, prior Baseline ICS use, and reason for therapy escalation will be summarized for the ITT population overall and by treatment group. Frequencies and percentages will be calculated for COPD drug class as defined in section 4.4.2 above.

Use of targeted COPD concomitant medications will be summarized at baseline. Frequencies and percentages will be calculated for Targeted COPD Concomitant Medications by COPD drug class as defined in section 4.4.2 above. Additionally, use of free versus FDC of triple therapy at baseline will be summarized for Triple Therapy patients.

EOS COPD treatment regimen will be summarized for the ITT population by treatment group, including frequencies and percentages by COPD drug class for Study COPD Medications and Targeted COPD Concomitant Medications as defined in section 4.4.2 above. Frequencies and percentages will also be calculated for Original Randomized Treatment and Step-Over In-Class Randomized Treatment at EOS.

# 5.5 Effectiveness Analysis

[figure not shown]
#### 5.5.1 Primary ITT Analysis

[figure not shown]
The primary effectiveness analysis will address the primary objective of this study: to compare the time to first moderate or severe COPD exacerbation between Stiolto Respimat and triple therapy. As the sample size is reduced (approximately 703 patients), the study is underpowered, so no test for non-inferiority of Stiolto Respimat compared to triple therapy will be performed. For the primary endpoint, COPD exacerbation defined as moderate or severe as collected in the eCRF will be used (section 4.5.1).

The primary analysis for the primary endpoint will be performed using the ITT population. Patients will be analyzed using the treatment arm to which they are randomized, even if they switched or discontinued study treatment. Patients will be censored at the time of last contact, death or day of planned EOS visit at 12 months (whichever occurs earlier), if they did not experience a moderate or severe COPD exacerbation before. This will be referred as ITT analysis.

For the primary endpoint, i.e. time to first moderate or severe COPD exacerbation, the Cox proportional hazards model with baseline ICS prior use as a covariate will be used to estimate the hazard ratio (HR) (Stiolto Respimat versus triple therapy), and the two-sided 95% Wald confidence interval (CI).

In addition, Kaplan-Meier curves will be presented with reported statistics including median survival time, as well as 95% CI for each group. If the median survival time is not reached, the first quartile will be reported instead.

# 5.5.3 Secondary Analyses

The secondary objectives of the study will be addressed through the secondary analyses detailed in the following sections. All secondary analyses will follow the ITT analysis as defined in Section 5.5.1 and will utilize the site-based exacerbation data from the eCRF.

#### 5.5.3.1 Annual Rate of Moderate or Severe Exacerbations

This analysis will address the secondary objective to compare the annual rate of moderate or severe COPD exacerbations for patients on Stiolto Respirat with patients on triple therapy.

The annual rate of moderate or severe exacerbations analysis will utilize a negative binomial model with fixed effect of treatment (Stiolto Respimat versus triple therapy), logarithm of observational time as offset, and baseline prior ICS use as a covariate. Observational time is defined as a patient's date of planned EOS at 12 months or last contact or death date (whichever occurs earlier) – Baseline visit date + 1 day. The rate ratio (Stiolto Respimat versus triple therapy) will be presented with 95% CI. Rates and 95% CI of each treatment group will also be presented.

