6.4 Effectiveness Analysis

The effectiveness analysis will address the primary objective of this study: to determine whether Stiolto Respimat is non-inferior to triple therapy as measured by time to first moderate or severe exacerbation. For the primary endpoint, COPD exacerbation defined as moderate or severe as collected in the eCRF will be used.

The primary analysis for the primary endpoint will be performed using the ITT population. Patients will be analyzed using the treatment arm to which they are randomized to, even if they switched or discontinued study treatment. Patients will be censored at the time of last contact or death, if they did not experience a moderate or severe COPD exacerbation before. The exacerbation data from eCRF will be used for the primary analysis.

For the primary endpoint, i.e. time to first moderate or severe COPD exacerbation, the Cox proportional hazards model with baseline ICS prior use as a covariate will be used to estimate the HR and the two-sided 95% Wald confidence interval.

The primary endpoint will also be analyzed for moderate or severe COPD exacerbations from different data sources: (1) claims data only and (2) integrated eCRF/claims data.

The details of all analyses will be fully described in the Statistical Analysis Plan (SAP).

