10 PUBLICATION OF STUDY RESULTS

All information related to this study is considered confidential information belonging to Boehringer Ingelheim and [REDACTED] A final study report will be generated following completion of data collection and analysis. Results and findings will be submitted to conferences and for publication in peer-reviewed scientific journals.

Table 1: Time and Events Schedule

Assessment or Procedure	Study Visits		
	Baseline	On Study Follow-Up¹	EOS 12 Months
Written Informed Consent	X		
Eligibility Criteria	X		
Randomization	X		
Demographics	X		
Selected pre-specified comorbid conditions	X		
CBC (Baseline Blood Eosinophil Count Required) ²	X		
Smoking Status	X		
COPD Diagnosis Date	X		
COPD Exacerbation History (number and severity of exacerbations in last year)	X		
Pre-Study COPD Therapy	X		
Reason for therapy escalation	X		
COPD Concomitant Medications	X	X	X
CAT TM	X		
Study Treatment	X	X	X
COPD Exacerbations		X	X
Selected AEs ³		X	X
SAEs ³		X	X

¹The only required study visits are Baseline and EOS. Data will be collected at routine clinical visits and other patient contact in between Baseline and EOS if available per standard clinical practice.

²In the event that a CBC is not available at baseline, laboratory results within 12 months of baseline will be accepted.

³All SAEs and selected AEs will be collected from Baseline through EOS or early termination of study participation. Selected AEs are AEs leading to study treatment discontinuation, dose modification or trial withdrawal.

Table 2: Sample size calculations (with number of events) under different assumptions for p1, HR and power, 20% non-inferiority margin, one-sided alpha 0.025 and 15% drop-out rate during 12 months.

Scenario	P1 (proportion of patients with >=1 moderate/severe COPD exacerbation during 12 months in Triple Therapy arm)	P2 (proportion of patients with >=1 moderate/severe COPD exacerbation during 12 months in Stiolto arm)	Expected HR of moderate/severe COPD exacerbations between Stiolto and Triple Therapy	Power	Number of events (moderate/severe COPD exacerbations)	Sample size (total)
1	40%	39.07%	0.97	95%	1147	3120
2	42.5%	42.5%	1	90%	1264	3200
3	45%	46%	1.03	80%	1358	3204

These sample size calculations were completed using Addplan 6.1 software based on a non-inferiority test for survival analysis.

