# 4.3 Missing Data

Except where otherwise noted, missing data will not be imputed and will be excluded from calculations.

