#### 4.4.4 COPD and Exacerbation History

Years with COPD will be calculated using Baseline visit date and COPD diagnosis date.

COPD exacerbation history will be collected at Baseline as the number of moderate COPD exacerbations in the past year and the number of severe COPD exacerbations requiring hospitalization in the past year. To enable GOLD A-D classification, the number of prior moderate and severe COPD exacerbations in the past year will be categorized as follows:

- Moderate Exacerbations (did not lead to hospitalization):  $0, 1, \ge 2$
- Severe Exacerbation (lead to hospitalization):  $0, \ge 1$

Additionally, to enable classification of a high risk subgroup, the following exacerbation history category will be defined:

•  $\geq$  2 Moderate or Severe Exacerbations

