# 5.5.3.4 Proportion of Patients with Moderate or Severe Exacerbations

This analysis will address the secondary objective to compare the proportion of patients with at least one moderate or severe COPD exacerbation from Baseline to the day of planned EOS visit at 12 months for patients on Stiolto Respimat with patients on triple therapy. The proportion of patients with a moderate or severe COPD exacerbation during the study observation period will be descriptively summarized overall, by treatment group, and by baseline prior ICS use. A Cochran-Mantel-Haenszel (CMH) model with baseline ICS prior use as stratum will be used to estimate the Risk Ratio (RR) (Stiolto Respimat versus triple therapy) and Risk Difference (Stiolto Respimat – triple therapy) of moderate or severe COPD exacerbations along with 95% CI. Unadjusted proportions will also be presented.

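### The exacerbation-rate model and the CMH analysis adjust only for prior ICS use; adding baseline exacerbation history would modestly narrow their intervals at no data cost

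*SAP*

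**What the plan says.** In SAP 5.5.3.1 the negative binomial model for moderate or severe exacerbations has a treatment effect, with "logarithm of observational time as offset, and baseline prior ICS use as a covariate". SAP 5.5.3.4 gives the analysis of proportions: "A Cochran-Mantel-Haenszel (CMH) model with baseline ICS prior use as stratum will be used to estimate the Risk Ratio (RR"), together with the risk difference. For the primary endpoint, Protocol 6.4 states that "the Cox proportional hazards model with baseline ICS prior use as a covariate will be used to estimate the HR", and SAP 5.5.1 says the same.

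Protocol Table 1 schedules this item at baseline: "COPD Exacerbation History (number and severity of exacerbations in last year"). SAP 4.4.4 provides that "the number of prior moderate and severe COPD exacerbations in the past year will be categorized as follows": moderate as 0, 1 or ≥2, and severe as 0 or ≥1. It also defines a combined category of at least two moderate or severe events. These variables feed the GOLD A–D classes (SAP 4.4.5) and the high-risk subgroup (SAP 4.4.8). They appear in none of the visible primary or secondary effectiveness models.

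**The concern.** The covariate left out is the patient's own count, over the previous year, of the event being analysed. The documents treat it as a marker of risk. Protocol 1.1 describes GOLD groups C and D as being at high risk of exacerbation, and SAP 4.4.5 separates C and D from A and B by history alone. Randomization is blocked (Protocol 6.3.2; SAP Appendix A), with no mention of stratification by history, so the design does not balance it.

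In the negative binomial model, patient-to-patient variation that history could explain stays in the dispersion. In the CMH analysis it stays in the binomial variance. SAP 2.1 drops the non-inferiority comparison and all p-values, so the estimates and their intervals are the whole effectiveness result, from about 703 patients instead of 3200. Precision lost for no reason is therefore worth recovering, even if the amount is modest.

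**Working it through.** **The plan's own figure.** Inputs from Protocol 6.3.1: true HR 1.0, margin 1.20, one-sided alpha 0.025, 90% power, 42.5% with an event in 12 months, 15% drop-out.
- Events = 4(1.960 + 1.282)² / (ln 1.2)² ≈ 1264, as in Table 2.
- With exponential event and drop-out hazards λ = −ln 0.575 and μ = −ln 0.85, P(observed event) = λ/(λ+μ) × (1 − 0.575 × 0.85) = 0.395. So N = 1264/0.395 ≈ 3200, as stated.
- At 703 patients this gives about 703 × 0.395 = 278 first events, and a Cox SE of √(4/278) = 0.120.

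The documents give no precision figure for the rate or proportion analyses.

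**Assumptions needed.** The documents state no history mix, dispersion or prognostic strength. Assumed: 45/30/25% of patients with 0/1/≥2 prior events; dispersion k = 0.5 given history; 351.5 patients per arm; no treatment effect; exponential drop-out reaching 15% at 12 months. The overall rate is solved so that 42.5% have an event over a full year. Four relative rates by history are used.

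**Rate ratio.** Information per arm = Σ μ/(1 + kμ), averaged over follow-up time; SE(log RR) = √(2/information). Without history the dispersion becomes (1 + k)(1 + CV²) − 1, where CV is that of the history effect.

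Third case (1/1.6/3) in full:
- Mean relative rate: 0.45 + 0.48 + 0.75 = 1.68. Mean square: 0.45 + 0.768 + 2.25 = 3.468.
- CV² = 3.468/1.68² − 1 = 0.229; unadjusted dispersion = 1.5 × 1.229 − 1 = 0.843.
- At an overall rate of 0.691 per year, information per arm is 143.4 without history and 161.3 with it. SEs are √(2/143.4) = 0.1181 and √(2/161.3) = 0.1113; variance ratio 0.889.

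| Later rates for 0/1/≥2 | Rate/year | SE without history | SE with history | Variance ratio | Simulated variance ratio | 95% CI around 1.0, without → with |
|---|---|---|---|---|---|---|
| 1/1.2/1.5 | 0.644 | 0.1132 | 0.1124 | 0.985 | 0.987 | 0.801–1.248 → 0.802–1.246 |
| 1/1.4/2 | 0.657 | 0.1146 | 0.1121 | 0.956 | 0.961 | 0.799–1.252 → 0.803–1.246 |
| 1/1.6/3 | 0.691 | 0.1181 | 0.1113 | 0.889 | 0.906 | 0.793–1.260 → 0.804–1.244 |
| 1/1.8/4 | 0.727 | 0.1214 | 0.1106 | 0.830 | 0.851 | 0.788–1.269 → 0.805–1.242 |

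The simulated column comes from about 400 fitted trials per case. On the SE scale the analytic gains are 0.8%, 2.2%, 5.7% and 8.9%. As extra patients, 703 × (1/ratio − 1), they are worth about 11, 32, 88 and 144. Over k from 0.3 to 1.5 and two other history mixes, the variance reductions run 1–2%, 4–6%, 9–14% and 13–23%.

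A second simulation used other mixes and dispersions, with prior ICS use in both models. SE(log RR) fell 0.5–7.5%, and by 2.7% and 4.8% in its middle scenarios (0.118 to 0.115; 0.121 to 0.115). With no history effect the SE did not change (0.1155 both ways).

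**Proportions.** Within-stratum over total binomial variance gives ratios for the risk difference of 0.992, 0.977, 0.943 and 0.911. In the second simulation, the SE of the log risk ratio fell 0.1–4.8% and that of the risk difference 0.7–5.4%.

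**Where there is little or no gain.** The severe-event rate model, at an assumed 0.1 per year, has variance ratios of 0.997, 0.992, 0.979 and 0.967. The Cox SE averages 0.120 with or without history. Adjustment moves the estimated HR by a median of 0.8%, 1.5%, 2.2% and 3.0%.

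**Chance imbalance.** If 25% have ≥2 prior events, the SD of the between-arm difference in that share is √(0.25 × 0.75 × 2/351.5) = 0.0327, so P(difference of 5 points or more) = 0.126. In the second case, patients with fewer than two events average (0.45 + 0.42)/0.75 = 1.16. Shares of 27.5% and 22.5% then give mean rates of 1.391 and 1.349, which shifts the rate ratio by about 3%.

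**The case against.** The strongest reply is that nothing turns on this. The planned intervals are valid, the endpoints are secondary, and SAP 2.1 has dropped all testing. In the two weaker cases the rate-ratio interval is 0.80–1.25 to two decimals with or without history. That stands, and it is why the gain is called modest. The prognostic strength is also assumed, and if it were nil the gain would be nil.

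A second reply is that the comparison above ignores the ICS adjustment already planned, which may capture part of the benefit if ICS use and history are correlated. This was checked by simulation, with ICS use in both models and correlated with history. The variance still fell by about 4% and 9% in the second and third cases.

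Third, chance imbalance is already reflected in the planned standard errors. That is correct. It is no separate source of bias, only a way in which the unadjusted estimate varies more.

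Fourth, parts of the SAP are not visible (5.5.2, for example), so a history-adjusted Cox sensitivity analysis may exist. Sections 5.5.3.1 and 5.5.3.4 can be read in full, however, and they name only prior ICS use.

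Finally, timing. Enrollment ended after August 2019, the SAP is dated March 2021, and under Protocol 6.3.2 the database is not blinded. A late choice of covariate could look data-driven. SAP 5.0 offers some protection: "Before the database lock, the team will review only table shells, not populated with actual data, to avoid bias". Whether lock has occurred must still be established first.

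**Conclusion.** The point holds as a matter of efficiency; it shows neither bias nor invalid intervals. The rate model and the CMH analysis leave out a baseline variable that is already collected and that the documents themselves treat as a marker of risk. At 703 patients, including it would reduce the variance of the log rate ratio by about 1.5% to 17% and that of the risk difference by about 1% to 9%, across the assumed history effects. These sizes depend on the assumed history mix, dispersion and prognostic strength. The change is worth making because it needs no new data, but the trial's conclusions do not depend on it. No gain in precision is claimed for the Cox models, and the gain for the severe-event rate is too small to pursue.

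**What to change.** Before database lock:

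1. In SAP 5.5.3.1, add prior-year moderate or severe exacerbations (0, 1, ≥2) as a covariate. SAP 4.4.4 categorizes moderate and severe events separately, so define the combined variable there from the two collected counts.
2. In SAP 5.5.3.4, add the same variable as a CMH stratum alongside prior ICS use.
3. Include a missing-history level in both. Under SAP 4.3, "missing data will not be imputed and will be excluded from calculations", so patients without history could otherwise drop out. Crossed with ICS use this makes up to eight CMH strata, some sparse; state how sparse strata will be combined.
4. Keep the ICS-only Cox model as primary in 5.5.1. Prespecify a history-adjusted Cox model as supportive, to show the effect of chance imbalance, without promising a narrower interval.
5. Leave the severe-event models unchanged. Section 5.5.3.3 describes its model as identical to that in 5.5.3.1; reword this so that the new covariate does not carry over.
6. Record the change and its reason in SAP 2.1. If the database is already locked, report the history-adjusted results as post hoc, beside the planned ones.

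The cost is a few extra parameters, a missing-history rule, adjustment sets that differ between endpoints, and a documented SAP change in an open-label trial. Protocol 6.4 names the ICS covariate only for the Cox model, which stays primary.
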